6 STUDY INTERVENTION

6.1 STUDY INTERVENTION(S) ADMINISTRATION

6.1.1 STUDY INTERVENTION DESCRIPTION

Aim 1: A Focus Group Discussion Guide will be finalized by the research team prior to recruitment (see Appendix 1 for example blank focus group data collection instrument). It will include questions to understand the relevance, feasibility and acceptability of: (1) using a taVNS device generally, (2) using it as treatment for PTSD, (3) the implementation protocol of the device, (4) the pilot study protocol (including the methodology details, timing, and both self-report, clinical, and biological assessments), and (5) the appropriateness of outcome measures. The estimated duration for the focus group is \approx 90 minutes. Drs. [name] and [name] will co-lead the focus group and the coordinator will take notes, write the minutes, and audio-record the session. [name] and/or [name] will demonstrate the device. Individuals will have the opportunity to handle the devices and there will be sanitizing wipes to be used in between. The focus group will be transcribed for qualitative analyses.

Aim 2:

Table 1. Aim 2 Outcome Measures	
Primary Outcome Measures (measured at 8 weeks)	
FEASIBILITY	
Recruitment	
-% responders who meet criteria 1-3 who accepted to come in for the CAPS interview (goal=33%)	
-% eligible responders who meet criteria 1-4 of those who came in for the CAPS interview (goal=66%)	
-% eligible responders who meet all criteria and were recruited and consented (goal = 75%)	
Retention	
-% participants who complete baseline and 8-wk measures (both survey and biological measures) (goal = 90%)	
Adherence	
-% participants who used taVNS 15 min/day once a day for 8 weeks (21 hours total) (goal=80%)	
Secondary Outcome Measures (measured at 8 weeks)	
ACCEPTABILITY	
Collection of Measures	
-Time (minutes) to fill out questionnaires (goal =<30 min)	
-Missing data from questionnaires: % items complete on the baseline and 8-wk self-report surveys (goal=90%)	
-Time (minutes) to collect biological data and blood draw (goal=10 min at baseline and 10 minutes at follow-up)	
-Rate of refusal of biologic measurements/blood draw (goal=5% refusal)	
Satisfaction	
-taVNS Intervention Study satisfaction survey (Adapted from Bakken et al.) (range=12-60; goal=100%-with score >47 among intervention group) ¹⁰⁰	
Tertiary Outcome Measures (measured at baseline and 8 week follow-up)	
Mental health symptoms (assessed to indicate signals for hypothesis generation)	

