-PTSD diagnosis and severity: CAPS interview ⁹⁵ (measured at screening and 8 week follow-up); PTSD Diagnosis: Yes/No; PTSD Severity score range=0-80)	
-PTSD symptom score (PCL-5 ⁹⁴ , range=0-80)	
-Anxiety symptom score (GAD-7 ¹⁰¹ , range=0-21)	
-Depression symptom score (PHQ-9 ¹⁰² , range=0-27)	
-Sleep score (Pittsburg Sleep Quality Index ¹⁰³ , range=0-21)	
Biologic Measures (assessed to indicate signals for hypothesis generation regarding potential mechanisms of action) At baseline, these will be measured 10 min before, during and 10 min after the initial taVNS administration	
-Heart rate/HRV (6-lead ECG, DI Powerlab) (beats/min, range=40-150)	
-EEG(DSI-24) (band-power dB changes, range=0-10)	
-Pupil Dilation (Tobii Pro Glasses 2) (pupil diameter in mm, range=2-8mm)	
-Galvanic Skin Response (GSR electrodes, ADI Powerlab) (skin conductance in microSiemens, range=0-50mS)	
-Skin Temperature (Thermistor Pod, ADI Powerlab) (Celcius, range=30-35C)	
-Respiratory Rate (Respiratory Belt, ADI Powerlab) (breaths per minute, range=3-20BPM)	
-Beat-to-Beat Blood Pressure (Human Non-Invasive Blood Pressure Nano Interface, ADI Powerlab) (mmHg, range=50-150mmHg)	
-Inflammatory Markers (blood draws at baseline before and after initial taVNS and at 6 week follow-up: TNFa, IL-1 β , IL-6, IL-10, IL-12, IL-17, CRP, Cortisol, Alpha Amylase)	
-Facial & Neck Electromyography (EMG electrodes, ADI Powerlab) (millivolts, range=0-15mV)	

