Procedure: After each of the 30 responders are enrolled (3 per month), they will be scheduled within that same month for an appointment at FIMR to be fitted with a custom-made taVNS device, a wearable TENS unit called the Nesos System. They will be compensated for their time/transportation. We expect to have approximately 1 visit per month for fittings, so that all 30 participants will be enrolled and fitted over 10 months. Participant visits will be staggered in order to protect privacy. After the devices are customized and delivered to FIMR (within approximately 1 month), responders will be called to FIMR for a baseline visit. One of the researchers from the Feinstein Institutes will assess the fit of the device and calibrate the level needed for each responder. At the baseline visit, responders will be given the device that matches their randomization sequence ID number. Each responder will also be given, along with the taVNS device, a locked-down Android Nexus 5X or Pixel phone to interface with the device and record the usage data. Responders will then be given a self-report survey to complete that asks demographic information, MH treatment-related information, and validated measures of MH and sleep (Table 1). Appendix 1 contains blank, sample self-report/interview measures. A research nurse will also collect 12 mL of blood to assess baseline and follow-up levels of inflammatory markers including Tumour Necrosis Factor alpha (TNF α), Interleukin (IL)-1 β , IL-6, IL-10, IL-12, IL-17, C Reactive Protein (CRP), cortisol, and alpha amylase. During the baseline visit, responders will also be shown how to use the device by Drs. [name] or [name]. The responders will use the device for one 15-minute session under the supervision of Drs. [name] or [name]. Biological non-invasive measures (not blood draw) of autonomic nervous system function and balance, as detailed in prior studies from the our group⁸⁰ and others, will be assessed 10 minutes before using the taVNS device. (see Table 1).

These non-invasive biological measures include: Respiratory belt, ECG, GSR, NIBP, EEG, Eye tracking.

Protocol Number: 21-0640

February 1, 2022

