The first sensor to be attached to the participant is a respiratory belt that goes around the torso. It is tightened without discomfort such that breathing causes the belt to stretch, which provides inspiration (inhalation) and expiration (exhalation) times to infer respiration rate. Next, the 6-lead electrocardiography (ECG) will be recorded from wires connected from a bio-amplifier, which gathers and increases physiologic signals, to four foam electrodes that are adhesively attached to the left shoulder, the right shoulder, the left ankle, and the right ankle. The right ankle provides a ground, while the remaining three leads provide recordings of the electrical potentials between different sites that represent the electrical activity of the heart in real-time.

Additional sensors are placed on the wrist and hands of the participant. The first set records galvanic skin response (GSR) by attaching two dry, metal electrodes with Velcro attachments on two fingers, preferably the pointer and ring fingers on the dominant hand. These electrodes measure the changes in skin conductance that can reflect changes in sweat gland activity. A wrist device will be placed to record non-invasive blood pressure (NIBP) from the middle finger on the participant's non-dominant hand. The wrist device is placed with a Velcro strap on the wrist, while a small cuff is placed on the middle finger. The wrist device provides air and power for the cuff to inflate and deflate to measure changes in blood pressure. A dry electrode electroencephalography (EEG) cap will be placed on the head of the participant. This cap offers low noise and high signal quality of non-invasive brain recordings without an uncomfortable cap that may require conductive gels. This cap can be placed on the head of the participant and record comfortably through hair without any gel. The final device to be placed on the participant is the eye tracking glasses. These are easily wearable and mobile glasses with multiple small cameras to track gaze and pupil size. If the participant wears prescription glasses, these will be removed and replaced with the eye tracking glasses (with the appropriate prescription lenses) for this study."

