Responders will then be instructed to use the device once a day, every day at home, for 15 minutes intervals over 8 weeks. The devices have a safety feature where they cannot be used for more than the intended timepoints daily and the stimulation parameter will be set by the investigator and cannot be altered by the participant. The date and time stamp of each use will be recorded on the application. The application only assesses usage/compliance and has no ability to capture any personal or other information. All phones containing the Nesos application is collected at the end of the study. Responders are requested to come in 8 weeks post-baseline and the same measures will be recorded again (self-report, biological and blood draw; see Table 1).

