8 STUDY ASSESSMENTS AND PROCEDURES

8.1 EFFICACY ASSESSMENTS

Aim 2: Primary Outcome Measure: Feasibility will be evaluated using criteria suggested by Leon⁹⁹: 1) rates of recruitment (per month), 2) adherence to the taVNS intervention, 3) 8-week retention, and 4) duration and completion rate of study assessments. Feasibility is defined as the ability to recruit 75% of eligible, approached, participants and to demonstrate intervention adherence and retention rates of 70% each (Table 1). **Secondary Outcome Measure:**

Protocol Number: 21-0640

February 1, 2022

Acceptability will be evaluated by assessing: 1) time to completion of questionnaires, 2) percentage of missing data from questionnaires, 3) time to completion of the biological data and blood draw, 4) rate of refusal of biologic measurements and blood draw, and 5) score on the taVNS Satisfaction and Usefulness Questionnaire¹⁰⁰ (Table 1). **Tertiary Outcome Measures** include potential taVNS endpoint measures. At the baseline and 8 week follow-up visits, validated self-report MH measures, including assessments of PTSD,⁹⁴ anxiety,¹⁰¹ depression,¹⁰² sleep,¹⁰³ and the CAPS interview⁹⁵ (at screener and follow-up) will be administered. To examine **potential mechanisms of action** and any acute and longer-term change in these mechanisms, the biological measures will be administered at baseline 10 minutes before using the device, again one time at the 8-week follow-up visit. Blood will be drawn to assess markers of inflammation before using the device, after using the device, and again at the 8 week follow-up visit. This allows us to collect data to understand potential acute and long-term effects. These tertiary outcome measures and potential mechanisms of action will be used to inform the

design of a future, RCT to evaluate taVNS efficacy. Measurement quality, amount of missingness or non-response, length of measurement collection, and costs will be assessed. These measures will also be used to provide parameter estimates for power calculations for a future RCT (Table 1). We will also use the preliminary efficacy results from this pilot to generate hypotheses regarding potential mechanisms of action including the various inflammatory, neural and cardiovascular changes that correlate with treatment outcomes

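### At baseline, the 10-minute goal for biological data and blood does not fit the protocol's own schedule, and the 100% satisfaction goal is missed by a single participant (minor)

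*Protocol*

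**What the plan says.** Acceptability is the secondary endpoint and has five measures (Sections 1.1, 3 and 8.1). Table 1 in Section 6.1.1 attaches a goal to each. Two matter here.

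- **Time.** "Time (minutes) to collect biological data and blood draw (goal=10 min at baseline and 10 minutes at follow-up". One figure covers recording and blood together, and it is the same at both visits.
- **Satisfaction.** "range=12-60; goal=100%-with score >47 among intervention group".

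On what is recorded at baseline, the protocol gives two accounts.

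- Table 1, biologic measures: "At baseline, these will be measured 10 min before, during and 10 min after the initial taVNS administration". The procedure text gives the session length: "The responders will use the device for one 15-minute session under the supervision".
- The same procedure text says the non-invasive measures "will be assessed 10 minutes before using the taVNS device", and Section 8.1 says "the biological measures will be administered at baseline 10 minutes before using the device, again one time at the 8-week follow-up visit". Sections 1.1 and 3 agree with this second account.

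For follow-up, Section 6.1.1 says only that "the same measures will be recorded again (self-report, biological and blood draw; see Table 1", with no duration.

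**The concern.** A time goal is useful as a benchmark only if the scheduled procedure can be done within it. Here one goal has to hold the recording, the set-up of six sensor systems and the blood draw. The protocol's own windows appear to fill or exceed it before set-up and blood are counted.

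The satisfaction goal has a different weakness. It allows no exception, so in a group of about 20 it is likely to be missed even if nearly everyone is content with the device.

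The pilot exists to inform a larger RCT, and the length of measurement collection is among the things it will assess. A time goal missed because of the schedule, or a satisfaction goal missed because of one person, could be read by the planners of that trial as evidence against acceptability.

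**Working it through.** **Time goal at baseline.** The protocol does not derive the 10 minutes, so the check sets it against the scheduled content.

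1. *Table 1 schedule.* Before 10 min + during 15 min + after 10 min = 35 min. Against the goal, 35 / 10 = 3.5. If the stimulation session is not counted as collection time, 10 + 10 = 20 min remain, still twice the goal. Both sums take the before and after figures as lengths of recording.
2. *Pre-device schedule (Sections 1.1, 3, 8.1 and the 6.1.1 procedure text).* If 10 minutes is the length of the recording, 10 − 10 = 0 min remain for set-up and blood. If it is a start time, the recording length is undefined and the goal cannot be checked.
3. *Set-up.* Section 6.1.1 describes sensors attached in turn, beginning "The first sensor to be attached to the participant is a respiratory belt that goes around the torso" and going on to ECG electrodes, skin-response electrodes, a wrist unit with finger cuff, an EEG cap and eye-tracking glasses. No minutes are given, but the time is not zero.
4. *Blood.* Table 1 and Section 8.1 have draws before and after the first session. Sections 2.3.1 and 3 describe one draw at baseline. On either account the draw falls inside the same 10 minutes.

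**Time goal at follow-up.** No recording length is stated, so there is nothing to add up.

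**Satisfaction goal.** The inputs are 30 participants (Section 9.3.1), 2:1 allocation (Section 6.3), and 90% expected retention (Section 9.1).

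- taVNS group: 30 × 2/3 = 20. At 90% retention: 20 × 0.9 = 18.
- One score of 47 or less among 20 gives 19/20 = 95%, and the goal is missed.
- If responses are independent and the true share above 47 is p, the chance that all n exceed 47 is pⁿ. The protocol gives no p, so it is varied.

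| Assumed true share p | n = 20 | n = 18 |
|---|---|---|
| 0.80 | 0.012 | 0.018 |
| 0.90 | 0.122 | 0.150 |
| 0.95 | 0.358 | 0.397 |
| 0.97 | 0.544 | 0.578 |
| 0.99 | 0.818 | 0.835 |

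An 80% chance of meeting the goal with n = 20 needs p = 0.8^(1/20) = 0.989.

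The other Table 1 goals allow some shortfall: 90% retention, 80% adherence, 90% of items complete and 5% refusal. As an illustration only, with n = 20 a goal of at least 18 (90%) would be met with probability 0.206, 0.677 and 0.925 at true shares of 0.80, 0.90 and 0.95. For at least 16 (80%) the figures are 0.630, 0.957 and 0.997.

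**The case against.** Four objections deserve an answer.

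- *The 35 minutes rests on one line of Table 1.* Sections 1.1, 3, 8.1 and the procedure text point to pre-device recording only, and the 10-minute goal may have been written for that schedule. This stands. On that reading the recording does not exceed the goal. It equals it, and the misfit comes from set-up and blood, whose minutes are not stated. A reader might also infer that the goal is too short at both visits, but no follow-up length is given, so that is not supported.
- *Missing a goal changes no stated conclusion.* This also stands. A reader might infer that the secondary endpoint is bound to come out as not acceptable. The documents do not support that. Fixed thresholds are part of the definition of feasibility only. Acceptability is assessed through five measures and described with percentages or means and 95% intervals. No stopping or progression rule uses these goals.
- *The satisfaction probabilities are assumptions.* True. At a share of 99% the goal is met about four times in five, so failure is not certain when the device is well liked. Only the arithmetic that one person suffices to miss it is free of assumptions.
- *Non-responders.* A reader might infer that anyone without a questionnaire makes the goal fail automatically. The protocol does not say that they count as failures. The 18 is itself approximate, because the retention goal also requires the biological measures.

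**Conclusion.** The point holds, and it is minor.

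At baseline, the 10-minute goal is inconsistent with the schedule in Table 1 (35 minutes, or 20 without the session). On the pre-device schedule it leaves no time for set-up or blood, provided the 10 minutes there is a duration. For follow-up the mismatch is unproven.

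The satisfaction goal is missed by one participant. With 20 assessed and independent responses, the chance of meeting it is 0.36, 0.12 and 0.01 at assumed true shares of 95%, 90% and 80%, and 0.82 at 99%.

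The consequence is a report of missed goals that could mislead the design of the next trial. The secondary endpoint does not fail because of it, and the primary feasibility thresholds are untouched.

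**What to change.** 1. Reconcile the baseline recording and blood-draw schedule across Sections 1.1, 2.3.1, 3, 6.1.1 (Table 1 and procedure text) and 8.1. State whether 10 minutes is a duration or a start time, and give the recording length at follow-up. The follow-up blood draw also needs reconciling: Table 1 places it at 6 weeks, Sections 3 and 8.1 at 8.
2. Then set the time goal for each visit as the fixed recording time plus a stated allowance for set-up and blood. Alternatively, apply the 10 minutes to set-up plus blood draw only, leaving out the fixed recording.
3. Replace the 100% satisfaction goal with a share below 100%, chosen by the sponsor in line with the other Table 1 goals. Base it on taVNS participants with a questionnaire and report the number without one. The particular figure is a matter of judgement that the documents do not settle.

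The cost is the schedule wording and two goals in Table 1, with no new data. The stated goals become slightly less ambitious. The change is best made before outcome data are seen, since a goal relaxed afterwards would carry little weight.

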6.1.2 ELECTRICAL STIMULATION AND ADMINISTRATION

The perceptual threshold will be determined at the initial session for every participant. This is 25% below the minimum amount of current required to perceive electrical stimulation on the skin at the target. Because of differences in the electrode-skin interface and anatomy of each individual, stimulation parameters will be adjusted for each participant to establish similar levels of activation over all participants.

A step-up and step-down binary parametric search will be used to establish the threshold and stimulation parameters. While delivering one second trains of stimulation, we will ask the participant whether s/he felt the stimulation. If yes, we reduce the stimulation intensity by 50%, while if no, we increase the stimulation intensity by 50%. This enables us to establish the minimum threshold for perception. Sensation is generally reported as a “tickle” or “pricking” sensation. Since taVNS is targeting a sensory nerve, perception and sensation remains the main indication that we are stimulating the auricular branch of the vagus nerve from locations on both the left and right ear.

6.2 HANDLING/STORAGE/ACCOUNTABILITY

6.2.1 ACQUISITION AND ACCOUNTABILITY

We will receive all taVNS devices at the Neural and Data Science Lab from Nesos Corp., where they will be kept in locked drawers, until they are handed out to the participants. Drs. [name] and [name] will be responsible for the timely acquisition and proper storage of the devices.

6.2.2 MANUFACTURING, PACKAGING, AND LABELING

The devices and all necessary components (stimulators, phones, ear mold and electrode materials) will be shipped to the Neural and Data Science lab as an investigational supply provided by the company. The company is listed as a consultant on our grant and we will be setting up a purchase order to provide them with a flat fee of funds in both year 1 and year 2.

The devices will bear the following labeling during the course of the study: “*CAUTION - Investigational device. Limited by Federal (or United States) law to investigational use*” per 21 CFR 812.5.

6.2.3 PRODUCT STORAGE

Information on each use of the device will be documented, and a Device Accountability Log will be maintained.

Protocol Number: 21-0640

February 1, 2022

Ear mold materials will be stored in a locked cabinet, inside a badge-access room of the Neural and Data Science lab. The ear molds will be fitted to the participants and each electrode will be connected to the external stimulator, and mobile app. The whole **Nesos System** will be put together by [name] from the Neural and Data Science lab or Nesos personnel and will be brought to the Device Training Visit (Visit 2)

6.2.4 DEVICE RISK DETERMINATION

Description of Transcutaneous Auricular VNS (taVNS) Intervention: The taVNS device that will be used in this study is a wearable Transcutaneous Electrical Nerve Stimulation (TENS) unit called the **Nesos System**. The **Nesos System**, which is manufactured by **Nesos Corp** in Redwood City, California, consists of a wearable, external stimulator, and a neural interface earpiece (Figure 2 below). The device is considered a non-significant risk device not requiring an Investigational Device Exemption (IDE). The wearable, external stimulator generates electrical pulses that are transcutaneously delivered to the auricular branch of the vagus nerve through the ear canal. The external stimulator is made out of Acrylonitrile Butadiene Styrene (ABS) plastic, which has a proven history of safe use in similar applications. The earpiece contains 4 electrodes that carry current from the external stimulator to the auricular branch of vagus nerve. The earpiece is made out of a silicone material that has evidence of safety in wearable devices. The electrode surface is made out of a medical grade, biocompatible conductive hydrogel or conductive silicone material

The system is comprised of the following major components:

- Stimulator – The stimulator is housed in an enclosure which is placed on the user's neck. It delivers charge-balanced, current-controlled, biphasic, square waves to electrodes (in the earbuds) in contact with the skin of the user's ear. The type of stimulation (total charge and energy delivered to the user) is comparable to the levels applied by commercially available transcutaneous electrical nerve stimulators (TENS) or non-invasive vagus nerve stimulators (nVNS).
- Earbuds – The earbuds are designed to transcutaneously-deliver electrical stimulation to the external ear. Each earbud is manufactured using ear molds unique to each user's ears to facilitate proper contact of the electrodes (in the earbuds) with the skin. Commercially available electrolyte solution (e.g., Signa spray or its equivalent) is recommended to be applied on the electrodes before they are placed in the ear. This conductive electrolyte solution reduces the electrode to skin interface resistance.
- Nesos proprietary APP – The system comes with a proprietary APP that is downloaded onto a smartphone. The key function of the APP is to allow the user to turn stimulation ON/OFF, monitor (using periodic impedance measurements) and notify the user of poor electrode/skin contact. In addition, the APP shows the amount of time left in a stimulation session and will notify the user when it is time for a session. The system also comes with a custom charging cable for recharging the stimulator.

Protocol Number: 21-0640

February 1, 2022

[figure not shown]
The Nesos MAUI PROTECT System was developed using a 13485:2016 ISO quality system and tested to ensure compliance with applicable clauses of standards.^{83,84} The Nesos MAUI PROTECT System delivers charge-balanced, current-controlled, biphasic, square waves to the auricular branch of the vagal nerve on the subject's skin. The type of stimulation (including shape, frequency, pulse width, amplitude, total charge and energy) delivered to the subject is comparable to the levels applied by commercially available TENS stimulators.

Although its use in this study is considered investigational, its use is considered to constitute minimal risk. It is also believed that its usage in this feasibility study meets the FDA definition of a non-significant risk device. The device is intended to be used to administer a low amount of current to stimulate the vagus nerve. The non-significant risk determination was made because the device does not constitute a significant risk device since it is not intended as an implant and does not present a potential for serious risk to the health, safety, or welfare of a subject; is not purported to be for use in supporting or sustaining human life and does not present a potential for serious risk to the health, safety, or welfare of a subject; is not for use of substantial importance in diagnosing, curing, mitigating, or treating disease and does not present a potential for serious risk to the health, safety, or welfare of a subject; and does not otherwise present a potential for serious risk to the health, safety, or welfare of a subject.

Figure 2. PROTECT System: A) Representative picture of a user with the wearable PROTECT System B) Components of the system include the stimulator housed within the over-the-neck enclosure, earbuds with integrated electrodes and a mobile APP

(A)

(B)

